7.4.1.2 Methods of Recording and Assessing Adverse Events

At each trial visit, the subject will be queried on changes in his/her condition. During the reporting period of the trial, any unfavorable changes in the subject's condition will be recorded as AEs, whether reported by the subject or observed by the Investigator.

Subjects will be asked to record information about any adverse reactions experienced between trial visits on their trial diaries (see Section 7.1.1). Diaries will be reviewed at each trial visit; information thus collected will be reviewed and assessed medically before it is transcribed to the CRF.

Complete, accurate and consistent data on all AEs experienced for the duration of the reporting period (defined below) will be reported on an ongoing basis in the appropriate section of the CRF. Among these AEs, all serious AEs must be additionally documented and reported using an Adverse Event Safety Report Form (Clinical Trial) as described in Section 7.4.1.4.

It is important that each AE report include a description of the event, its duration (onset and resolution dates (and times, if relevant)), its severity, its relationship with the trial treatment, any other potential causal factors, any treatment given or other action taken (including dose modification or discontinuation of the IMP), and its outcome. In addition, serious cases should be identified and the appropriate seriousness criteria documented.

Because of the i.a. route of administration used and the expectation that the great majority of the injected drug will remain within the knee joint, Investigators must classify each reported AE as "local (i.e., concerning only the knee that is treated)" or "systemic" in the subject's CRF to permit separate evaluation of AEs classified as local and AEs classified as systemic.

Specific guidance can be found in the CRF Completion and Monitoring Conventions provided by the Sponsor.

7.4.1.3 Definition of the Adverse Event Reporting Period

The AE reporting period for safety surveillance begins when the subject is included into the trial (date of first signature of informed consent) and continues until the end of the trial's post-treatment extended follow-up phase, or until the subject's final trial visit in case of early withdrawal.

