5.5 Criteria for Subject Withdrawal

5.5.1 Withdrawal from the Trial

Subjects are free to discontinue the trial at any time without giving their reasons.

The Investigator may withdraw a subject at any time if this is considered to be in the subject's best interest.

A subject must be withdrawn in the event of any of the following:

- Withdrawal of the subject's consent
- Subject's participation in another trial

If a subject fails to attend scheduled trial assessments, the Investigator must determine the reasons and the circumstances as completely and accurately as possible.

In case of premature withdrawal from the trial, the procedures scheduled for Week 104/Visit 22 should be performed at the time of withdrawal whenever possible, with focus on the most relevant assessments. In any case, the appropriate Case Report Form section must be completed.

Subjects who withdraw from the trial will not be replaced.

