7.1.5 Follow-Up in Case of Early Termination

Early Treatment Discontinuation

Subjects who discontinue treatment prematurely will undergo the assessments planned for Week 104/Visit 22 at the time of discontinuation (see [Appendix E](#)). If they are willing to continue in the trial, they will undergo all subsequent assessments planned for the remainder of their trial

participation (Visit 23 through Visit 28; with no further administration of IMP). Subjects who discontinue participation during the extended follow-up phase should have Week 260/Visit 28 procedures completed whenever possible.

Early Trial Withdrawal

Subjects who withdraw from the trial should undergo the assessments planned for Week 104/Visit 22 at the time of withdrawal whenever possible (see [Appendix E](#)).

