7.4.1.4 Procedure for Reporting Serious Adverse Events

In the event of any new SAE occurring during the reporting period, the Investigator must immediately (i.e., within a maximum 24 HOURS after becoming aware of the event) inform the Sponsor's GDS department by fax or by e-mail.

Reporting procedures and timelines are the same for any new information on a previously reported SAE (i.e., follow-up).

For names, addresses, telephone and fax numbers for SAE reporting, see information included in the Adverse Event Safety Report Form (Clinical Trials).

All written reports should be transmitted using the Adverse Event Safety Report Form (Clinical Trials), which must be completed by the Investigator following specific completion instructions.

Relevant pages from the CRF may be provided in parallel (e.g., medical history, concomitant medications). In all cases, the information provided in the Adverse Event Safety Report Form (Clinical Trials) must be consistent with the data on the event that are recorded in the corresponding sections of the CRF.

The Investigator/Reporter must respond to any request for follow-up information (e.g., additional information, outcome and final evaluation, specific records where needed) or to any question the Sponsor may have on the AE within the same timelines as described for initial reports. This is necessary to permit a prompt assessment of the event by the Sponsor and (as applicable) to allow the Company to meet strict regulatory timelines associated with expedited safety reporting obligations.

Requests for follow-up will usually be made by the responsible Monitor, although in exceptional circumstances the GDS department may contact the Investigator directly to obtain clarification or to discuss a particularly critical event.

7.4.1.5 Safety Reporting to Health Authorities, Independent Ethics Committees/ Institutional Review Boards and Investigators

The Sponsor will send appropriate safety notifications to Health Authorities in accordance with applicable laws and regulations.

The Investigator must comply with any applicable site-specific requirements related to the reporting of SAEs (and in particular deaths) involving his/her subjects to the IEC/IRB that approved the trial.

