7.4.1.6 Monitoring of Subjects with Adverse Events

Any AE that occurs during the course of a clinical trial and is considered to be possibly related to the IMP must be monitored and followed up by the Investigator until stabilization or until the outcome is known, unless the subject is documented as “lost to follow-up”. Reasonable attempts to obtain this information must be made and documented. It is also the responsibility of the Investigator to ensure that any necessary additional therapeutic measures and follow-up procedures are performed. The Sponsor will actively follow up and collect information on any AE that occurs during the course of a clinical trial; however, while this activity will continue for any serious AEs until stabilization or until the outcome is known, it will be discontinued at the time of database lock for non-serious AEs.

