7.4.2 Pregnancy and In Utero Drug Exposure

Only pregnancies considered by the Investigator as related to trial treatment (e.g., resulting from a drug interaction with a contraceptive medication) are considered as AEs. However, all pregnancies with an estimated conception date during the period defined in Section 7.4.1.3 must be recorded by convention in the AE page/section of the CRF. The Investigator must notify the Sponsor in an expedited manner of any pregnancy using the Pregnancy Report Form, which must be transmitted according to the same process as described for SAE reporting in Section 7.4.1.4.

Investigators must actively follow up, document and report on the outcome of all these pregnancies, even if the subjects are withdrawn from the trial.

The Investigator must notify the Sponsor of these outcomes using the Pregnancy Report Form, and in case of abnormal outcome, the Adverse Event Safety Report Form (Clinical Trials) when

the subject sustains an event, and the Parent-Child/Fetus Adverse Event Report Form when the child/fetus sustains an event.

Any abnormal outcome must be reported in an expedited manner as described in Section 7.4.1.4, while normal outcomes must be reported within 45 days from delivery.

In the event of a pregnancy in a subject occurring during the course of the trial, the subject must be discontinued from trial medication immediately. The Sponsor must be notified without delay and the subject must be followed as mentioned above.

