17.1 Adverse Events

Adverse Events will be coded using latest version of MedDRA at the end of each of 2 reporting periods (2 year and 5 year analyses).

For 2 years analysis: Treatment-emergent adverse events (TEAEs) are defined as those adverse events that either start or worsen in severity on or after the date of first dose of study treatment (first injection) until 30 days from last dose of study treatment (last injection). Where dates are missing or partially missing, adverse events will be assumed to be treatment-emergent, unless there is clear evidence (through comparison of partial dates) to suggest that the adverse event started prior to the first dose of study treatment or after the subject's last treatment (+30 days). See appendix 20.4 for details.

For 5 years analysis: All AEs from the complete duration of the study will be summarized (but not TEAEs, as these are not relevant per definition above). There will be no summaries of TEAEs for the 5 years analysis only AE

Pre-treatment emergent adverse events, i.e. adverse events starting between date of informed consent and until date of first dose of study treatment will be tabulated separately.

Adverse events of special interest (AESI) will include the following:

Injection site reactions will be summarized by treatment group and PT. These will be identified using higher level term (HLT) "Injection site reactions".

Similarly, musculoskeletal complaints (eg. Back pain, neck pain), will be identified using prespecified SOC "Musculoskeletal and connective tissue disorders" and will be summarized by treatment group and by PT.

In addition, Neoplasms will be identified using pre-specified SOC "Neoplasms benign, malignant and unspecified (including cysts and polyps)" and will be summarized by treatment group and by PT.

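### For subjects who withdraw from the trial, adverse event collection can stop before the SAP's 30-day treatment-emergent window has closed

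*Protocol*

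**What the plan says.** Protocol section 7.4.1.3 runs the AE reporting period from consent to the end of the extended follow-up phase or, for subjects who leave, to the "final trial visit in case of early withdrawal". Section 7.4.1.2 limits what is recorded in the CRF to that period. Section 7.4.1.4 applies the same limit to serious events: "In the event of any new SAE occurring during the reporting period".

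Subjects may leave at any time. Section 5.5.1 says that "the procedures scheduled for Week 104/Visit 22 should be performed at the time of withdrawal whenever possible", and section 7.1.5 repeats it: "Subjects who withdraw from the trial should undergo the assessments planned for Week 104/Visit 22 at the time of withdrawal whenever possible". Neither section names a minimum time after the last injection or a later safety contact. Subjects who only stop the IMP and agree to stay continue with the extended follow-up visits, so their AE collection continues.

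For the 2-year analysis, SAP section 17.1 counts events that start or worsen from the first injection "until 30 days from last dose of study treatment (last injection"). SAP section 17.1.1 reports numbers and percentages of subjects, and the Safety Analysis Set (SAP section 10) keeps everyone who received at least one dose.

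**The concern.** The SAP analyses a window that the protocol does not fully collect. A subject who leaves shortly after an injection stays in the denominator of every treatment-emergent table, and the uncollected days count as event-free.

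Those days come just after an intra-articular injection, when local reactions matter most. Protocol section 3 reports that actively treated subjects in the proof-of-concept trial appeared to have slightly more acute inflammatory reactions. It also reports one potentially treatment-related serious event, bacterial arthritis, in a placebo subject. At stake are the completeness of early post-injection safety data for these subjects and the ability to see whether shortened windows are balanced across arms.

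**Working it through.** **1. Does another provision close the gap?**

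- Section 7.4.1.6: an AE that occurs during the trial and is "considered to be possibly related to the IMP must be monitored and followed up by the Investigator until stabilization". This follows events already within scope and does not lengthen the period for collecting new ones.
- Section 5.5.1: when a subject misses assessments, "the Investigator must determine the reasons and the circumstances as completely and accurately as possible". This concerns why the subject stayed away and is not AE collection.
- Sections 7.1.1 and 7.1.3: reminder calls concern analgesic washout and diary completion. Diaries are collected at the following visit, which a leaver may not attend.
- Section 7.4.2: pregnancies are followed "even if the subjects are withdrawn from the trial", but only those conceived within the 7.4.1.3 period. Section 6.5.1 sets no contraception requirement after the last visit. This is a smaller point.
- SAP section 17.1: the missing-date rule classifies recorded events and cannot recover unrecorded ones.

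None of these closes it.

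**2. Days lost by final visit.** Days lost = max(0, 30 − days since last injection), using the visit weeks in Protocol section 5.1.

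| Final visit | Days since last injection | Days lost |
|---|---|---|
| 12 injection visits, if dosed | 0 | 30 |
| Weeks 3, 29, 55, 81 | 7 | 23 |
| Weeks 12, 38, 64, 90 | 70 | 0 |
| Week 104 | 168 | 0 |

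So 16 of the 21 treatment-phase visits leave a shortfall. If the subject withdraws before dosing at the visit, 12 of 21 still lose 23 days.

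**3. How many subjects?** Protocol section 8.1 needs 76 evaluable subjects per group: 76/0.70 = 108.6, so 109 per group and 545 in total, which matches the plan. Planned dropout is 0.30 × 545 = 163.5. The documents give neither the share who leave the trial nor the timing. Assume first that all of them leave, evenly over 4 × 182 = 728 days.

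- Injections fall on days 1, 8 and 15 of each cycle. Departure days 0 to 29 days after the latest injection: 7 + 7 + 30 = 44 per cycle, so 176 of 728 (24.2%).
- Subjects leaving inside a window: 163.5 × 176/728 = 39.5, or 7.9 per arm. If half of dropouts leave the trial, 19.8; if a quarter, 9.9.

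**4. How much is lost?**

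- Visit on the day of leaving: (14 × 27 + 30 × 15.5)/44 = 843/44 = 19.2 days on average. 39.5 × 19.2 gives 757 subject-days (unrounded inputs).
- No withdrawal visit: the last scheduled visit is an injection day for 21 departure days (30 days lost) and the one-week visit for 23 (23 days lost). (21 × 30 + 23 × 23)/44 = 1,159/44 = 26.3 days, giving 1,041 subject-days.

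Total window days:

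- Completers: 381.5 × 591 = 225,467 (last injection on day 561, plus 30).
- Dropouts: the mean cycle start is day 274, and the latest injection is on average (7 × 0 + 7 × 7 + 168 × 14)/182 = 13.2 days later. Adding 30 gives 317.2, and 163.5 × 317.2 = about 51,860.
- Sum: about 277,300. The losses are 757/277,300 = 0.27% and 1,041/277,300 = 0.38%.

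The no-visit figure is conservative. Subjects who leave on the 40 days per cycle after the window closes but before the next visit, and who also skip the withdrawal visit, have the one-week visit as their last and lose 23 days too. They are not counted.

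**The case against.** The SAP rule can be read as a classification by onset date that does not promise 30 days of observation for everyone. On that reading, any crude incidence table with dropout treats unobserved time as event-free, and the months of dosing and follow-up that early leavers miss matter more. This is fair, and the fix does not address that larger inequality. It does not change the fact that the protocol stops collecting before the SAP's own window ends.

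The size is small and assumed. The documents give no timing of withdrawals, no split between stopping IMP and leaving, and no contact rate. This stands, so the figures above are a scenario and not an estimate.

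The group that can be helped is narrow. Willing subjects can stay in follow-up, those who withdraw consent may refuse contact, and those lost to follow-up are hard to reach. The 30-day loss also requires that the subject was dosed at the last visit and never returned. These points limit the gain but do not remove it.

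The withdrawal visit is a full Week 104 safety assessment, and an AE that causes departure should surface as the reason for withdrawal. That covers events up to leaving, not those that begin afterwards.

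**Conclusion.** The concern holds. The gap is in the protocol text, and no provision in the documents fills it. It applies only to subjects who leave the trial, and only when their final visit falls less than 30 days after their last injection.

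The expected size is about 10 to 40 subjects, as between a quarter and all of the planned dropout leaves the trial at even timing. It would be more if withdrawals cluster after injections. The effect on overall treatment-emergent rates is small. This is a worthwhile low-cost improvement to safety capture and does not threaten the trial's conclusions.

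**What to change.** Amend Protocol sections 7.4.1.3, 5.5.1 and 7.1.5 so that new AEs, SAEs and pregnancies are collected until the later of the final trial visit or 30 days after the last injection. For withdrawn subjects who have not refused contact, one phone call suffices. Add to the SAP section 12 disposition table, per arm, the number of subjects whose AE follow-up ended less than 30 days after the last injection. The dates behind SAP sections 12 and 15 already allow that count, but no planned table shows it.

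The cost is one sentence carried into three sections, with whatever submission and renewed consent Protocol section 10.5 requires, one table row, and roughly 10 to 40 calls. If 50% to 80% of these subjects could be reached (an assumption), the calls would complete about 20 to 32 windows of 40, or 5 to 8 of 10. Those who cannot be reached probably include many who skip the withdrawal visit.

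Timing matters. The SAP records full enrolment by September 2014 and was finalised in August 2016. An amendment made that late would reach few or no dosed subjects, but the per-arm count would still be available.

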7.4.1.4 Procedure for Reporting Serious Adverse Events

In the event of any new SAE occurring during the reporting period, the Investigator must immediately (i.e., within a maximum 24 HOURS after becoming aware of the event) inform the Sponsor's GDS department by fax or by e-mail.

Reporting procedures and timelines are the same for any new information on a previously reported SAE (i.e., follow-up).

For names, addresses, telephone and fax numbers for SAE reporting, see information included in the Adverse Event Safety Report Form (Clinical Trials).

All written reports should be transmitted using the Adverse Event Safety Report Form (Clinical Trials), which must be completed by the Investigator following specific completion instructions.

Relevant pages from the CRF may be provided in parallel (e.g., medical history, concomitant medications). In all cases, the information provided in the Adverse Event Safety Report Form (Clinical Trials) must be consistent with the data on the event that are recorded in the corresponding sections of the CRF.

The Investigator/Reporter must respond to any request for follow-up information (e.g., additional information, outcome and final evaluation, specific records where needed) or to any question the Sponsor may have on the AE within the same timelines as described for initial reports. This is necessary to permit a prompt assessment of the event by the Sponsor and (as applicable) to allow the Company to meet strict regulatory timelines associated with expedited safety reporting obligations.

Requests for follow-up will usually be made by the responsible Monitor, although in exceptional circumstances the GDS department may contact the Investigator directly to obtain clarification or to discuss a particularly critical event.

7.4.1.5 Safety Reporting to Health Authorities, Independent Ethics Committees/ Institutional Review Boards and Investigators

The Sponsor will send appropriate safety notifications to Health Authorities in accordance with applicable laws and regulations.

The Investigator must comply with any applicable site-specific requirements related to the reporting of SAEs (and in particular deaths) involving his/her subjects to the IEC/IRB that approved the trial.

In accordance with ICH GCP guidelines, the Sponsor will inform the Investigator of “findings that could adversely affect the safety of subjects, impact the conduct of the trial or alter the IEC’s/IRB’s approval/favorable opinion to continue the trial.” In particular and in line with respective regulations, the Sponsor will inform the Investigator of AEs that are both serious and unexpected and are considered to be related to the administered product (“suspected unexpected serious adverse reactions” or SUSARs). The Investigator should place copies of Safety reports in the Investigator Site File. National regulations with regard to Safety report notifications to Investigators will be taken into account.

When specifically required by regulations and guidelines, the Sponsor will provide appropriate Safety reports directly to the concerned lead IEC/IRB and will maintain records of these notifications. When direct reporting by the Sponsor is not clearly defined by national or site-specific regulations, the Investigator will be responsible for promptly notifying the concerned IEC/IRB of any Safety reports provided by the Sponsor and of filing copies of all related correspondence in the Investigator Site File.

For trials covered by the European Directive 2001/20/EC, the Sponsor’s responsibilities regarding the reporting of SAEs/SUSARs/Safety Issues will be carried out in accordance with that Directive and with the related Detailed Guidances.

7.4.1.6 Monitoring of Subjects with Adverse Events

Any AE that occurs during the course of a clinical trial and is considered to be possibly related to the IMP must be monitored and followed up by the Investigator until stabilization or until the outcome is known, unless the subject is documented as “lost to follow-up”. Reasonable attempts to obtain this information must be made and documented. It is also the responsibility of the Investigator to ensure that any necessary additional therapeutic measures and follow-up procedures are performed. The Sponsor will actively follow up and collect information on any AE that occurs during the course of a clinical trial; however, while this activity will continue for any serious AEs until stabilization or until the outcome is known, it will be discontinued at the time of database lock for non-serious AEs.

7.4.2 Pregnancy and In Utero Drug Exposure

Only pregnancies considered by the Investigator as related to trial treatment (e.g., resulting from a drug interaction with a contraceptive medication) are considered as AEs. However, all pregnancies with an estimated conception date during the period defined in Section 7.4.1.3 must be recorded by convention in the AE page/section of the CRF. The Investigator must notify the Sponsor in an expedited manner of any pregnancy using the Pregnancy Report Form, which must be transmitted according to the same process as described for SAE reporting in Section 7.4.1.4.

Investigators must actively follow up, document and report on the outcome of all these pregnancies, even if the subjects are withdrawn from the trial.

The Investigator must notify the Sponsor of these outcomes using the Pregnancy Report Form, and in case of abnormal outcome, the Adverse Event Safety Report Form (Clinical Trials) when

the subject sustains an event, and the Parent-Child/Fetus Adverse Event Report Form when the child/fetus sustains an event.

Any abnormal outcome must be reported in an expedited manner as described in Section 7.4.1.4, while normal outcomes must be reported within 45 days from delivery.

In the event of a pregnancy in a subject occurring during the course of the trial, the subject must be discontinued from trial medication immediately. The Sponsor must be notified without delay and the subject must be followed as mentioned above.

